7.2 General Methodology

Summary statistics for continuous variables will be represented by number of subjects(n), mean, median, standard deviation and categorical variables will be represented by counts and percentages. P-values for hypothesis testing will be evaluated based on one-sided testing using significance level of 0.025. Confidence intervals if needed will be reported as two-sided 95% confidence intervals. For primary safety, primary effectiveness and secondary effectiveness endpoints, normality will be verified for appropriate statistical methodology. Comparisons between the outcomes in study period and the threshold will be performed using one sample T-test for testing the statistical significance of the difference if normality assumption is met or Wilcoxon signed rank test if normality assumption is not met. In addition, the mean, median, min, and max will be presented when the normality assumption is not met.

The templates for Tables, Listings and Figures (TLFs) will be available in the TLFs document.

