4.2.3 Secondary Effectiveness Endpoint

- Age 18-80: The mean % of time in hypoglycemia (< 54 mg/dL [3.0 mmol/L]) will be estimated and compared to a threshold of 0.86% by a non-inferiority test with a margin of 2% and a significance level of 0.025 (one-sided).
- Age 18-80: The mean % of time in range (TIR 70-180 mg/dL [3.9 -10.0 mmol/L]) will be estimated and compared to a threshold of 73.7% by a simple superiority test and a significance level of 0.025 (one-sided).
- Age 7-17: The mean % of time in hypoglycemia (< 54 mg/dL [3.0 mmol/L]) will be estimated and compared to a threshold of 0.71% by a non-inferiority test with a margin of 2% and a significance level of 0.025 (one-sided).
- Age 7-17: The mean % of time in range (TIR 70-180 mg/dL [3.9 -10.0 mmol/L]) will be estimated and compared to a threshold of 65.3% by a simple superiority test and a significance level of 0.025 (one-sided).

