7.9.1 Pass/Fail Criteria

- The goal of the study for each age cohort (age 18-80 and age 7-17) is to evaluate both primary safety and primary/secondary effective endpoints according to the predefined threshold per cohort. Once all effective endpoints are met, the claim of superiority will be made.
- The goal of study for each age cohort (age 18-80 and age 7-17) will be also considered met when the evaluation criteria of both primary safety and effective endpoints meets the predefined threshold per cohort. However, the claim of non-inferiority will not be made.

Justification for Exclusion of Particular Information from the testing of the Hypothesis: Not Applicable.

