7.9.2 Primary Safety Endpoint

Age 18-80:

[figure not shown]
The overall mean change in HbA1c, $\Delta\mu_{780G}$, from baseline to end of 3-month study period will be estimated and compared by a non-inferiority test to the threshold of -0.50% with a margin of 0.4%⁴. A significance level of 0.025 (one-sided) will be used. Analysis will be performed on the ITT and PP populations.

The hypothesis of non-inferiority is mathematically expressed as:

 H_0 : $\Delta \mu_{780G} \ge -0.50\% + 0.4\%$

 H_a : $\Delta \mu_{780G} < -0.50\% + 0.4\%$

17-JUN-2024 Revision 4.0 Page 19 of 25

The null hypothesis will be tested against the alternative hypothesis using one sample t test if normality assumption is met, Wilcoxon signed rank test if normality assumption is rejected. Non inferiority of MiniMed 780G system utilizing insulin Fiasp (insulin aspart injection) for age 18-80 will be concluded if null hypothesis is rejected.

Age 7-17:

The overall mean change in HbA1c, $\Delta \mu_{780G}$, from baseline to end of 3-month study period will be estimated and compared by a non-inferiority test to the threshold of -0.38% with a margin of 0.4%⁴. A significance level of 0.025 (one-sided) will be used. Analysis will be performed on the ITT and PP populations.

The hypothesis of non-inferiority is mathematically expressed as:

$$H_0$$
: $\Delta \mu_{780G} \ge -0.38\% + 0.4\%$

$$H_a$$
: $\Delta \mu_{780G} < -0.38\% + 0.4\%$

The null hypothesis will be tested against the alternative hypothesis using one sample t test if normality assumption is met, Wilcoxon signed rank test if normality assumption is rejected. Non inferiority of MiniMed 780G system utilizing insulin Fiasp (insulin aspart injection) for age 7-17 will be concluded if null hypothesis is rejected.

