7.9.3.1 Primary Effectiveness Endpoint

Age 18-80:

[figure not shown]
The mean % of time, µ_{780G}, in range (TIR 70-180 mg/dL [3.9 -10.0 mmol/L]) will be estimated and compared by a non-inferiority test to the threshold of 73.7% with a margin of 7.5%^{5,6}. A significance level of 0.025 (one-sided) will be used. The 7.5%, which is approximately 100 minutes increase in TIR per day, was also observed from the HCL pivotal trials. It is loosely correlated to ~0.5% reduction in A1c as well. Analysis will be performed on the ITT and PP populations.

The hypothesis of non-inferiority is mathematically expressed as:

 H_0 : $\mu_{780G} \le 73.7\% - 7.5\%$

 H_a : $\mu_{780G} > 73.7\% - 7.5\%$

17-JUN-2024 Revision 4.0

Page 20 of 25

The null hypothesis will be tested against the alternative hypothesis using one sample t test if normality assumption is met, Wilcoxon signed rank test if normality assumption is rejected. Non inferiority of MiniMed 780G system utilizing insulin Fiasp (insulin aspart injection) for age 18-80 will be concluded if null hypothesis is rejected.

Age 7-17:

The mean % of time, μ_{780G} , in range (TIR 70-180 mg/dL [3.9 -10.0 mmol/L]) will be estimated and compared by a non-inferiority test to the threshold of 65.3% with a margin of 7.5%^{5,6}. A significance level of 0.025 (one-sided) will be used. The 7.5%, which is approximately 100 minutes increase in TIR per day, was also observed from the HCL pivotal trials. It is loosely correlated to ~0.5% reduction in A1c as well. Analysis will be performed on the ITT and PP populations.

The hypothesis of non-inferiority is mathematically expressed as:

 H_0 : μ_{780G} ≤ 65.3% − 7.5%

 H_a : $\mu_{780G} > 65.3\% - 7.5\%$

The null hypothesis will be tested against the alternative hypothesis using one sample t test if normality assumption is met, Wilcoxon signed rank test if normality assumption is rejected. Non inferiority of MiniMed 780G system utilizing insulin Fiasp (insulin aspart injection) for age 7-17 will be concluded if null hypothesis is rejected.

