7.9.4 Analysis of Secondary Effectiveness Endpoints

Age 18-80:

Secondary Effectiveness Endpoint: The mean % time, μ_{780G}, in hypoglycemia (< 54 mg/dL [3.0 mmol/L]) will be estimated and compared by a non-inferiority test to the threshold of 0.86% with a margin of 2%⁷. A significance level of 0.025 (one-sided) will be used. Analysis will be performed on the ITT and PP populations. The 2% came from not more than 30 minutes increase in hypoglycemia per day to establish a non-inferiority test.

The hypothesis of non-inferiority is mathematically expressed as:

 H_0 : $\mu_{780G} \ge 0.86\% + 2\%$

 H_a : $\mu_{780G} < 0.86\% + 2\%$

The null hypothesis will be tested against the alternative hypothesis using one sample t test if normality assumption is met, Wilcoxon signed rank test if normality assumption is rejected. Non inferiority of

17-JUN-2024 Revision 4.0 Page 21 of 25

Form Medtronic

MiniMed 780G system utilizing insulin Fiasp (insulin aspart injection) for age 18-80 will be concluded if null hypothesis is rejected.

Secondary Effectiveness Endpoint: The mean % of time, μ_{780G} , in range (TIR 70-180 mg/dL [3.9 -10.0 mmol/L]) will be estimated and compared by a simple superiority test with a significance level of 0.025 (one-sided). Analysis will be performed on the ITT and PP populations.

The hypothesis of superiority is mathematically expressed as:

 H_0 : $\mu_{780G} \le 73.7\%$

 H_a : $\mu_{780G} > 73.7\%$

The null hypothesis will be tested against the alternative hypothesis using one sample t test if normality assumption is met, Wilcoxon signed rank test if normality assumption is rejected. Superiority of MiniMed 780G system utilizing insulin Fiasp (insulin aspart injection) for age 18-80 will be concluded if null hypothesis is rejected.

Age 7-17:

Secondary Effectiveness Endpoint: The mean % time, μ_{780G}, in hypoglycemia (< 54 mg/dL [3.0 mmol/L]) will be estimated and compared by a non-inferiority test to the threshold of 0.71% with a margin of 2%⁷. A significance level of 0.025 (one-sided) will be used. The 2% came from not more than 30 minutes increase in hypoglycemia per day to establish a non-inferiority test. Analysis will be performed on the ITT and PP populations.

The hypothesis of non-inferiority is mathematically expressed as:

 H_0 : $\mu_{780G} \ge 0.71\% + 2\%$

 H_a : $\mu_{780G} < 0.71\% + 2\%$

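### Hypotheses about means are tested with a Wilcoxon signed-rank test when normality fails, so the one-sided 0.025 level is not held for skewed data

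*SAP*

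**What the plan says.** SAP 7.2 sets the level: "P-values for hypothesis testing will be evaluated based on one-sided testing using significance level of 0.025". For the primary safety, primary effectiveness and secondary effectiveness endpoints it says that "normality will be verified for appropriate statistical methodology". It then uses a one-sample t-test if normality is met, "or Wilcoxon signed rank test if normality assumption is not met".

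The endpoint sections repeat the rule: 7.9.2 (HbA1c change) has "Wilcoxon signed rank test if normality assumption is rejected", 7.9.3.1 (primary TIR) has "using one sample t test if normality assumption is met, Wilcoxon signed rank test if normality assumption is rejected", and 7.9.4 (time below 54 mg/dL and TIR superiority) has "one sample t test if normality assumption is met, Wilcoxon signed rank test if normality assumption is rejected". In each, the null and alternative are written on a mean, and non-inferiority or superiority is concluded when that null is rejected by whichever test was chosen.

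Protocol 4.2.3 also frames the endpoint as a mean: "The mean % of time in hypoglycemia (< 54 mg/dL [3.0 mmol/L]) will be estimated and compared to a threshold of 0.86"%. SAP 7.9.1 ties the labelling-type claim to these tests: "Once all effective endpoints are met, the claim of superiority will be made". No visible section restates a hypothesis on a median or pseudomedian, or assumes symmetry.

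**The concern.** The signed-rank test holds its level when the data are symmetric about the threshold. Under skew the pseudomedian and the mean differ, and the rule chooses this test when normality fails, which includes skewed data.

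The direction of the error follows the skew:

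- **Inflated:** left-skewed TIR (rejects for high values); right-skewed HbA1c change and right-skewed time below 54 mg/dL (both reject for low values).
- **Conservative:** the opposite skew in each case.

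Because the normality criterion is unnamed, the step that decides which quantity is tested is itself not pre-specified.

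The most exposed result is TIR superiority. It has no margin, so its boundary is the threshold itself, and it is the last step before the superiority claim. SAP 7.5.1 and 7.5.2 run each step of the fixed sequence at the full 0.025, so error control within a cohort relies on every test holding its level. The HbA1c primary test is exposed if the true mean change lies near its limit.

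**Working it through.** **Inputs from the documents.** One-sided level 0.025 (SAP 7.2). About 100 subjects per cohort (SAP 6.1). Null boundaries on the mean (SAP 7.9.2 to 7.9.4):

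| Endpoint | Age 18-80 | Age 7-17 | Rejects for |
|---|---|---|---|
| HbA1c change | -0.50 + 0.40 = -0.10% | -0.38 + 0.40 = +0.02% | low values |
| TIR non-inferiority | 73.7 - 7.5 = 66.2% | 65.3 - 7.5 = 57.8% | high values |
| Time <54 mg/dL | 0.86 + 2 = 2.86% | 0.71 + 2 = 2.71% | low values |
| TIR superiority | 73.7% | 65.3% | high values |

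**Assumptions.** The normality check is Shapiro-Wilk; p < 0.05 leads to Wilcoxon, otherwise the t-test. n = 100. TIR follows a beta distribution on 0-100% with SD 8, 10 or 12, or a shifted gamma with SD 10 to set the skewness. HbA1c change is a shifted gamma with SD 0.6. Time <54 mg/dL is a gamma with CV 0.75, 1.0 or 1.25.

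**Method.** Draw samples whose true mean equals the boundary, apply the rule, and count one-sided rejections at 0.025. TIR and HbA1c used 10,000 replicates; at a rate of 5% the Monte Carlo SE is √(0.05 × 0.95 / 10,000) = 0.0022, or about 0.2 points. Time <54 mg/dL used 5,000 replicates.

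**Step 1, reproduce the stated level.** With normal data and n = 100: t-test 0.0243, Wilcoxon 0.0238, full rule 0.0238. With symmetric t data on 5 degrees of freedom: t-test 0.0238, Wilcoxon 0.0240. The level holds under symmetry, so what follows is due to skew.

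**Step 2, TIR superiority.** For a beta with mean 0.737 and SD 0.10, a + b = 0.737 × 0.263 / 0.01 - 1 = 18.38, which gives skewness -0.47. SD 8 and 12 give -0.38 and -0.55.

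| Adult, 73.7% | SD 8 | SD 10 | SD 12 |
|---|---|---|---|
| Normality rejected | 28% | 45% | 66% |
| SAP rule | 4.3% | 5.5% | 6.2% |
| Always Wilcoxon | 5.3% | 6.1% | 6.5% |
| Always t-test | 3.0% | 3.0% | 2.8% |

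Ages 7-17 at 65.3%: the rule gives 3.5 / 3.7 / 3.5%. Adults with skewness set directly to -0.5 / -0.8 / -1.0: 5.6 / 9.1 / 12.9% (t-test 3.1 to 3.3%). With +0.5 / +1.0: 1.4 / 0.4%.

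**Step 3, primary TIR.** The rule gives 2.9 to 4.2% at 66.2% and 2.6 to 2.9% at 57.8% (beta model).

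**Step 4, HbA1c change.** Skewness +0.5 / +1.0: 4.7 / 12.7% at -0.10% and 5.3 / 13.6% at +0.02% (t-test 2.8 to 3.8%). Skewness -0.5 / -1.0: 1.5 / 0.3% and 1.8 / 0.3%. Differences between the two limits are simulation noise, since only the location changes.

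**Step 5, time <54 mg/dL.** CV 0.75 / 1.0 / 1.25: the rule gives 24 / 38 / 54% at 2.86% (t-test 4.1 / 3.9 / 5.4%) and 23 / 38 / 53% at 2.71%. Larger samples make it worse: at CV 1.0 and 2.71%, always-Wilcoxon error is 0.318 with n = 80 and 0.452 with n = 125. A bootstrap-t test of the mean at 2.86% gives 2.7 / 2.8 / 3.0% (4,000 replicates, SE 0.3 points).

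**Step 6, away from the boundary.** With true adult TIR one point below 73.7%, the rule passes in 0.2 to 1.6% of trials. With true time <54 mg/dL at 0.86% or 1.5%, the rule and the t-test both pass in 100%. At CV 1.0 they separate at 2.0% (100% against 96%) and at 2.5% (83% against 34%).

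**The case against.** The strongest reply is about size, since the mismatch between hypothesis and test is plain in the text.

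- **Primary TIR is barely affected** (2.6 to 4.2%). This stands. HbA1c change is the other endpoint that decides success, and there the sign of the skew is unknown; left skew makes the rule conservative.
- **The largest figures are the least relevant.** The 23 to 54% for time <54 mg/dL needs a true mean more than three times the threshold (2.86 / 0.86 = 3.3). This stands: the rule is invalid at that boundary, but a mean near 0.86% passes either way.
- **The 9 to 13% TIR figures need more skew than the bounded model gives.** A beta with mean 73.7% needs an SD of about 20 to reach skewness -0.8. This stands, so 3.5 to 6.2% is the better guide for TIR superiority.
- **The window for a false superiority claim is narrow.** One point below the threshold, the pass rate is already under 2.5%. True, but a test's level is defined at the boundary, and here the boundary is the threshold on which the claim rests.
- **Missing SDs may be redacted.** Fair for the SDs, which are treated here as assumptions. SAP 7.2 appears intact, so the absence of a normality criterion is a fair reading.
- **The SAP also presents mean and median when normality fails.** That lets a reader see a divergence, but it does not change which test decides.

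**Conclusion.** The concern holds. As written, the rule does not test the stated mean hypotheses at one-sided 0.025 when the data are skewed. The practical size is modest: about 4 to 6% for adult TIR superiority and about 3.5% for ages 7-17 under a bounded model. It is larger for HbA1c change only if the change is right-skewed and its true mean is near the limit. The error can run in either direction.

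These figures rest on n = 100, the assumed SDs and skewness, and an assumed Shapiro-Wilk check at 0.05. Another normality criterion would give a rate roughly between always-t and always-Wilcoxon, which is 2.8 to 6.5% for adult beta TIR. The point should be fixed before analysis because it bears on the superiority claim and on the fixed sequence, and because the choice of test is currently open.

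**What to change.** In SAP 7.2 and 7.9.2 to 7.9.4, test the mean for every endpoint whatever the normality result, and remove the normality check as a gate.

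- **HbA1c change and TIR:** one-sample t-test.
- **Time <54 mg/dL:** a skewness-robust one-sided 97.5% upper bound on the mean, such as bootstrap-t, compared with 2.86% or 2.71%.
- **Medians and Wilcoxon results:** keep as labelled descriptive or sensitivity output.

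Restating the hypotheses on the pseudomedian and using Wilcoxon throughout would also remove the mismatch, but the thresholds and margins, now written for means, would then need justification on that scale.

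The cost is SAP wording and a few lines of code, with no new data or subjects. Some p-values for skewed data become slightly less favourable. The t-test stays mildly off nominal under strong skew: up to about 3.8% for HbA1c change and 3.3% for TIR in these runs.

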7.3 Center Pooling

Data will be pooled for analysis.

7.5 Adjustments for Multiple Comparisons

The following hierarchical test procedure reflects the relative importance of the endpoints and controls for multiplicity. Safety and effectiveness endpoints will be evaluated independently between age 18-80 and age 7-17.

Fixed sequential testing of primary safety, primary effectiveness and secondary effectiveness endpoints for age 18-80 and age 7-17. The pass/fail criteria (see section 7.9.1) are established independently for each age cohorts.

[figure not shown]
7.5.1 Age 18-80

For the following endpoints from age 18-80, the procedure test hierarchically the ordered hypotheses in sequence at level $\alpha = 0.025$ until a first hypothesis is non-rejected.

Primary Safety Endpoint

 Age 18-80: The overall mean change in HbA1c from baseline to end of 3-month study period. The goal is to show non-inferiority with a margin of 0.4%⁴ comparing to a threshold of -0.5% in reducing HbA1c from baseline to end of 3-month study period.

17-JUN-2024 Revision 4.0 Page 17 of 25

Primary Effectiveness Endpoint

Age 18-80: The mean % of time in range (TIR 70-180 mg/dL [3.9 -10.0 mmol/L]) will be estimated and compared to a threshold of 73.7% by a non-inferiority test with a margin of 7.5%^{5,6} and a significance level of 0.025 (one-sided).

Secondary Effectiveness Endpoints

- Age 18-80: The mean % of time in hypoglycemia (< 54 mg/dL [3.0 mmol/L]) will be estimated and compared to a threshold of 0.86% by a non-inferiority test with a margin of 2%⁷ and a significance level of 0.025 (one-sided).
- Age 18-80: The mean % of time in range (TIR 70-180 mg/dL [3.9 -10.0 mmol/L]) will be estimated and compared to a threshold of 73.7% by a simple superiority test and a significance level of 0.025 (one-sided).

7.5.2 Age 7-17

For the following endpoints from age 7-17, the procedure test hierarchically the ordered hypotheses in sequence at level $\alpha = 0.025$ until a first hypothesis is non-rejected.

Primary Safety Endpoint

 Age 7-17: The overall mean change in HbA1c from baseline to end of 3-month study period. The goal is to show non-inferiority with a margin of 0.4%⁴ comparing to a threshold of -0.38% in reducing HbA1c from baseline to end of 3-month study period.

Primary Effectiveness Endpoint

Age 7-17: The mean % of time in range (TIR 70-180 mg/dL [3.9 -10.0 mmol/L]) will be estimated and compared to a threshold of 65.3% by a non-inferiority test with a margin of 7.5%^{5,6} and a significance level of 0.025 (one-sided).

[figure not shown]
Secondary Effectiveness Endpoints

- Age 7-17: The mean % of time in hypoglycemia (< 54 mg/dL [3.0 mmol/L]) will be estimated and compared to a threshold of 0.71% by a non-inferiority test with a margin of 2%⁷ and a significance level of 0.025 (one-sided).
- Age 7-17: The mean % of time in range (TIR 70-180 mg/dL [3.9 -10.0 mmol/L]) will be estimated and compared to a threshold of 65.3% by a simple superiority test and a significance level of 0.025 (one-sided).

7.6 Demographic and Other Baseline Characteristics

Subject characteristics, including age, gender, race, ethnicity, medical diagnosis, height, weight, Body Mass Index (BMI), and baseline HbA1c will be summarized by descriptive statistics (mean, standard deviation, minimum, median, and maximum) for continuous variables and by counts and percentages for categorical variables.

17-JUN-2024 Page 18 of 25 Revision 4.0

7.7 Treatment Characteristics

Not applicable.

7.8 Interim Analyses

Not applicable.

7.9 Evaluation of Objectives

Safety and effectiveness endpoints will be evaluated independently between age 18-80 and age 7-17.

7.9.1 Pass/Fail Criteria

- The goal of the study for each age cohort (age 18-80 and age 7-17) is to evaluate both primary safety and primary/secondary effective endpoints according to the predefined threshold per cohort. Once all effective endpoints are met, the claim of superiority will be made.
- The goal of study for each age cohort (age 18-80 and age 7-17) will be also considered met when the evaluation criteria of both primary safety and effective endpoints meets the predefined threshold per cohort. However, the claim of non-inferiority will not be made.

Justification for Exclusion of Particular Information from the testing of the Hypothesis: Not Applicable.

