6.4 Guardian 4 Sensor

The Guardian 4 sensor, referred to as the sensor in this protocol, is a sensor that contains one microelectrode with a thin coating of glucose oxidase beneath several layers of biocompatible membrane. The Guardian 4 sensor will be used with the 780G system. The sensor is the latest generation of glucose sensor with design changes for supporting improved accuracy. It is intended to penetrate the skin at a 90-degree angle. The sensor is tubeless. An introducer needle penetrates the skin surface and provides support for the sensor microelectrode during insertion. The sensor continuously converts small amounts of glucose from the subject's interstitial fluid into an electronic signal that is received by a transmitter or recorder, the strength of which is proportional to the amount of glucose present in the blood. The electrode is composed of embedding, signal-conducting and insulating layers.

CIP336 Clinical Investigation Plan Medtronic D00459338 Version E Page 48 of 159

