3.1 Background

In patients with insulin dependent diabetes mellitus, glycemic control is influenced by numerous factors such as insulin dosage, insulin absorption, timing, physiological/ lifestyle factors such as exercise, food intake, hormones and illness. These factors may contribute to significant variability in insulin requirements, which makes self-management of type 1 diabetes challenging.

Patients who are using continuous glucose monitoring (CGM), including sensor-augmented pump therapy, experience improvements in glycemic control. Advanced sensor-augmented insulin pumps are now being used in clinical practice including closed loop systems that automatically adjust the amount of insulin delivered to maintain glucose levels near the target value set by the user.¹

The MiniMed 780G system is a closed loop insulin system. In addition to automatically adjusting the amount of insulin delivered based on sensor glucose (SG) readings while operating in the SmartGuard feature, the MiniMed 780G insulin pump can also automatically deliver correction boluses when the system has been delivering at the maximum allowable basal rate and SG remains elevated. This pump is currently in commercial distribution in Canada, Australia, and the United States. Previous clinical investigations involved the 670G Version 4.0 pump (contains the 780G AHCL algorithm) used in combination with the Guardian Sensor (3) glucose sensor, Guardian Link 3 transmitter, Humalog and Novolog insulin. This investigation is intended to confirm safety and effectiveness of the 780G insulin pump used in combination with Fiasp insulin. Additional details for non-clinical/clinical testing are provided in the report of prior investigations/ Investigator's Brochure (IB).

3.2 **Purpose**

The purpose of this study is to evaluate the safety and effectiveness of the MiniMed 780G system in type 1 adult and pediatric subjects utilizing Fiasp (insulin aspart injection) in a home setting.

Study Objectives 4.

The objective of this study is to evaluate the safety and effectiveness of the MiniMed 780G system utilizing insulin Fiasp (insulin aspart injection) to support product and system labeling.

[figure not shown]
Investigational Plan - Study Design 5.

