This global study is a multi-center, single arm study in insulin-requiring adult and pediatric subjects with type 1 diabetes on the MiniMed 780G system using Fiasp insulin as well as Medtronic Extended infusion set and reservoir. The run-in period and study period will be approximately 120 days long.

The period from Visit 1 (consent and screening) through Visit 6 should be completed in 30 days.

Companions:

17-JUN-2024 Revision 4.0 Page 6 of 25

Subjects will be required to have a companion who resides (or will live) in the same building (or home) during the study at night, and also to be physically present in the same building, home or location (if not at home) during the exercise and meal challenges. A companion should be present during meal challenges and for 4 hours following the start of the meal. Companions should be able to check SMBG, give glucose and/or administer glucagon.

Run-in Period (Visits 2-6):

The run-in period begins at Visit 2 and ends once Visit 7 occurs.

The intent of the run-in period will be to allow subjects to become familiar with new study devices while using their own insulin, either Humalog™ (insulin lispro injection) or NovoLog®/NovoRapid® (insulin aspart solution for injection). During the run-in period, study subjects with prior Automated Insulin Delivery (AID) control algorithm experience will be using the study pump with the SmartGuard feature activated (Auto Correction must remain OFF). and Medtronic Extended infusion set and reservoir. Subjects who do not have prior AID algorithm experience will use the system in Manual Mode. Before and during run-in period meal challenges, SmartGuard must be turned OFF, as noted in Meal Challenge instructional materials.

Note for subjects who have prior experience with the Auto Mode feature in Medtronic pumps (670G/770G): The term "Auto Mode" has been replaced by the term "SmartGuard" in the 780G pump.

During the run-in period, a 120 mg/dL (6.7 mmol/L) Auto Basal target should be set. It is recommended that Active Insulin Time is set to 4 hours.

Note: The Auto Basal target setting and Active Insulin Time should be set as recommended above, unless there is a documented safety reason that would not permit these settings to be used.

[figure not shown]

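### The SAP turns a single-arm test of mean time in range against a fixed threshold into an unqualified superiority claim; the test supports only that the threshold was exceeded

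*SAP*

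**What the plan says.** SAP Section 5 describes the design: "This global study is a multi-center, single arm study in insulin-requiring adult and pediatric subjects". There is no control group. Under SAP 7.2, "P-values for hypothesis testing will be evaluated based on one-sided testing using significance level of 0.025", using a one-sample t test, or a Wilcoxon signed rank test if normality is rejected.

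The hypotheses in each cohort are tested in a fixed order, and TIR superiority comes last. In SAP 7.5.1 the adult mean is to be "compared to a threshold of 73.7% by a simple superiority test". SAP 7.5.2 does the same for ages 7-17 with 65.3%.

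Two places turn that test into a conclusion:

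- SAP 7.9.1: "Once all effective endpoints are met, the claim of superiority will be made".
- SAP 7.9.4: "Superiority of MiniMed 780G system utilizing insulin Fiasp (insulin aspart injection) for age 18-80 will be concluded" if the null is rejected, with a parallel sentence for ages 7-17.

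Neither says what the system is superior to. The protocol is narrower. Sections 4.2.3 and 14.5.2.2 set out the threshold test and its hypotheses, and the pass/fail rule in 14.5.2.1 rests on the primary endpoints only. None of these sections makes a superiority claim.

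**The concern.** In ordinary use, superiority is a comparative word. A conclusion that the 780G system with Fiasp is superior, with no comparator named, invites the reading that Fiasp outperforms other rapid-acting insulins in this pump, or that this system outperforms its predecessors. The stated objective is to support product and system labeling, so the wording of the conclusion matters.

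Nothing in the design isolates either comparison. SAP 3.1 says the earlier investigations used the 670G Version 4.0 pump, "used in combination with the Guardian Sensor (3) glucose sensor, Guardian Link 3 transmitter", with Humalog and Novolog. This trial uses Fiasp and the Guardian 4 sensor, which protocol 6.4 calls the "latest generation of glucose sensor with design changes for supporting improved accuracy". TIR is computed from sensor readings, so the measuring instrument differs as well as the insulin. SAP 7.9.3 limits effectiveness data to the period from Visit 13 onward, when the Auto Basal target and Active Insulin Time are individualised at the investigator's discretion. The settings used in the earlier investigations are not described. A difference from any earlier result could not be attributed to the insulin or the system.

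**Working it through.** **Inputs.** One-sided alpha 0.025 (SAP 7.2). Thresholds 73.7% and 65.3% (SAP 7.5.1, 7.5.2). About n = 100 per cohort, from a minimum of 100 in each age group and 200 entering the study period (SAP 6.1). The visible text gives no SD for TIR and no source or sample size for the thresholds, so anything that uses them below is an assumption.

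**Step 1: reproduce the stated error rate.** The null is mean TIR ≤ 73.7%, with 73.7 a constant. The nominal error is 1 − Φ(1.960) = 0.025. A simulation of the one-sample t test with normal data, n = 100 and true mean 73.7 rejected in 0.0252 of 200,000 runs. Fixed-sequence testing keeps 0.025 within each cohort, so the plan's figure is confirmed for the hypothesis it states.

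This applies to the t test. The Wilcoxon fallback addresses location under symmetry rather than the mean, so its error for a skewed TIR distribution is a separate question.

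**Step 2: set the hypothesis beside the conclusion.**

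| | What it refers to |
|---|---|
| Alternative hypothesis (SAP 7.9.4) | Cohort mean TIR above 73.7% (65.3%) |
| What rejection establishes | The same |
| Conclusion drawn (SAP 7.9.1, 7.9.4) | Superiority of the system with Fiasp, comparator unnamed |

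The third row goes beyond the second.

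**Step 3: what a comparative reading would do to the error rate.** Suppose the threshold is the mean of m earlier subjects with the same SD, and the claim concerns the therapy behind it. The difference then has variance SD²/n + SD²/m, but the test allows only for SD²/n. The real one-sided error is

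1 − Φ(1.96 / √(1 + n/m)).

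With n = 100:

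| m (assumed) | 1.96 / √(1 + n/m) | Real one-sided error |
|---|---|---|
| 50 | 1.132 | 0.129 |
| 100 | 1.386 | 0.083 |
| 200 | 1.600 | 0.055 |
| 1000 | 1.869 | 0.031 |

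Holding 2.5% at m = 100 would need a critical value of 1.96 × √2 = 2.77. At an assumed SD of 10 the standard error is 10/√100 = 1.0, so the observed excess would have to be about 2.8 TIR points instead of 2.0. These figures show what a comparative claim would require. They are not error rates of the test as written.

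**Step 4: check 7.9.1 against the neighbouring sections.** The second bullet of SAP 7.9.1 treats the goal as also met when the primary safety and effectiveness endpoints meet their thresholds, but says that non-inferiority will not be claimed. SAP 7.9.2 and 7.9.3.1 say that non-inferiority is concluded whenever the corresponding primary null is rejected. Protocol 14.5.2.1 calls a cohort successful on those same two endpoints. Read literally, the study could succeed by rejecting non-inferiority nulls and yet not claim non-inferiority. The bullet may have been meant to withhold superiority instead, but the text does not say so.

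**The case against.** The best defence is that the plan never claims superiority over another insulin or system. Every TIR test is defined against a threshold, 7.9.1 itself refers to the predefined threshold for each cohort, and testing against a performance goal is conventional in single-arm device studies. On that reading, superiority is shorthand for exceeding the goal. This stands as a defence of the test, but not of the wording. The conclusion sentences in 7.9.4 drop the threshold and attach superiority to the system using Fiasp, and 7.9.1 makes this a claim to be issued rather than a test label.

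A reader might infer two stronger points that the documents do not support.

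- *The real type I error exceeds 2.5%.* The figures in Step 3 replace the stated null with a comparative one and assume a historical sample size and an equal SD. The documents do not say that the thresholds are estimates, or that they came from the investigations described in SAP 3.1. The protocol's sample-size section and some SAP sections named in its revision history (7.4, 7.9.5 and 7.9.6) are not visible. The source and precision of the thresholds may be given there, so their absence is not counted against the plan.
- *The newer sensor inflates the error.* With n = 100 and an assumed SD of 10, a 1-point upward shift gives a rejection probability of about 0.17. But if mean TIR truly exceeds 73.7%, rejecting is correct for the stated null, whatever the cause. A 1-point shift the other way gives 1 − Φ(2.96), about 0.0015. The protocol speaks of improved accuracy and gives neither the direction nor the size of any effect on measured TIR.

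The protocol also needs no change to its test, because 4.2.3 and 14.5.2.2 only define it.

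**Conclusion.** The concern holds as a point about the conclusion, not the test. SAP 7.9.1 and 7.9.4 would produce an unqualified superiority claim from evidence that supports one statement per cohort: mean TIR exceeded 73.7% (65.3%). With no concurrent comparator, and with sensor, transmitter, pump version and insulin all different from the earlier investigations described, superiority over another insulin or system cannot be concluded.

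The 2.5% error stands for the t test of the threshold hypothesis. The value 0.083 applies only if the claim is taken as comparative and the threshold was estimated from an equal-sized sample with the same SD. Both conditions are assumptions, and the wording point does not depend on them. The conflict over non-inferiority in 7.9.1 is plain from the text. Overall this is a cheap improvement.

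**What to change.** In SAP 7.9.1 and in both age-cohort parts of 7.9.4, replace the superiority claim and conclusion with: *mean TIR exceeded the prespecified performance goal of 73.7% (age 18-80) or 65.3% (age 7-17)*. Report the mean with its two-sided 95% CI, the interval format already set in SAP 7.2. Add one sentence stating that no superiority over another insulin or system is claimed.

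In the same revision, reconcile the 7.9.1 sentence on not claiming non-inferiority with SAP 7.9.2 and 7.9.3.1 and with the pass/fail rule in protocol 14.5.2.1, so that each combination of endpoint results leads to one stated conclusion. The tests in protocol 4.2.3 and 14.5.2.2 stay as they are.

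The cost is SAP wording only. Sample size, data collection, the tests and alpha do not change. The downside for the sponsor is a more modest label statement.
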